4.2 Inclusion Criteria

1. Healthy women of 18 years of age or older and non-childbearing potential (i.e., prior hysterectomy or bilateral tubal ligation; last menstrual cycle more than 12 months prior to

study enrollment or serum FSH >40 IU/L if woman has not had a bilateral tubal ligation or hysterectomy).

2. Clinical symptoms of overactive bladder for 6 months or longer including at least one of the following:
 - a. Frequent micturition ≥ 8 times per 24 hrs
 - b. Symptoms of urinary urgency (the complaint of sudden compelling desire to pass urine, which is difficult to defer) or nocturia (the complaint of *waking* at night two or more times to void)
 - c. Urge urinary incontinence five or more incontinence episodes per week based on 7-day voiding diary. Urge urinary incontinence is defined as: the complaint of involuntary leakage accompanied by or immediately preceded by urgency.
3. Detrusor overactivity with ≥ 1 uncontrolled phasic contraction(s) of the detrusor of at least 5 cm/ H₂O pressure documented on cystometry at Screening Visit 1A (i.e., prior to study drug administration at Visit 2).
4. Bladder scan or direct catheter drainage demonstrating a residual volume of ≤ 200 ml
5. Non-response or response but poor tolerance to a previous treatment for symptoms of overactive bladder/urinary incontinence (e.g., anti-muscarinic/ anticholinergic agents, or Botox) or do not wish to continue these treatments.
6. Able to understand study requirements (i.e., literate in English), give written informed consent, and comply with all study procedures and requirements.

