5.2.1 Stopping Rules

No acute toxicity was seen in the preclinical studies in rats with administered intravenous doses up to 1000 µg (approximately 1500 µg/kg in the rat). Potential toxicities would be those that could occur (1) because of enhanced efflux of K^+ with resultant decreased intracellular Ca^{++} concentration, thus altering smooth muscle function in diverse organ systems; (2) reaction to the naked DNA.

In the event that any participant experiences one of the following events, **no** additional participants will be accrued and **no** further doses of hMaxi-K will be administered until the DSMB and FDA have reviewed the case and have provided their recommendation to the sponsor.

- 1) Urinary retention, i.e., the inability to micturate for more than 12 hours with a urine bladder volume (greater than 400 ml established by bladder scan) that requires placement of a bladder drainage catheter.
- 2) Any adverse event of Grade 2 that last longer than 96 hours or Grade 3 or higher in the blood chemistry, completed blood count or urine categories of adverse event criteria listed in Appendix A.
- 3) In the event of a clinically significant sign or symptom reported by the site PI to the medical monitor in any of the first four participants of each cohort unless permission is given by the medical monitor.
- 4) Bladder pain and /or irritation that persists for four hours or more after gene transfer that is thought by the Principal Investigator not to be related to acute trauma from the cystoscopy, direct bladder muscle injections, and catheterization.

Clinical data regarding the event will be collected, reviewed, and discussed with DSMB and FDA. After review of these data with FDA the clinical study may resume **only** with concurrence of FDA.

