6. ANALYSIS POPULATIONS

Safety Analysis Population: For safety analyses, the Safety Population will be used. This population consists of subjects who have been dosed including partial/incomplete doses.

Efficacy Population will be used to for efficacy analyses. This population include subjects who are dosed and have at least one post-dose efficacy assessment.

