7.5. Handling of Dropouts or Missing Data

Handling of missing concentration data will be detailed in PK analysis plan and/or report. Missing data for adverse events, laboratory test will not be imputed. Last observation carried forward (LOCF) will be used to impute efficacy endpoints.

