9. EFFICACY ANALYSES

9.1. Primary Efficacy Analyses

The per participant listing for voiding diary (Dispense Daily Voiding Diary/Urgency Questionnaire) will be presented in Listing 16.2.6.1. The cystometry overread parameters will be presented in Listings 16.2.6.2.1 and 16.2.6.2.2, and in Listings 16.2.6.2.3 through 16.2.6.2.5 for site investigator read. The bladder scan per subject will be detailed in Listing 16.2.6.3 and the pad test in Listing 16.2.6.4. The QoL survey will be presented in two listings with King's Health Questionnaire (KHQ) in Listing 16.2.6.5.1 and SF-12 in Listing 16.2.6.5.2. Per participant assessment of disease and response to treatment will be detailed in Listing 16.2.6.6. Also, participant response to International Consultation on Incontinence Questionnaire (ICIQ) Short Form will be presented in Listing 16.2.6.7. The primary efficacy result, the reduction of the number of voids per day compared to placebo using voiding diary data, will be presented in Table 14.2.1.1. Assuming the number of voids follows a normal distribution, we will test whether there is significantly more reduction in the treatment group at each time point, where there are difference between treatment groups for the pooled *h*Max-K group vs. the placebo group using linear mixed effect model adjusting for the clustering effect by each individual with treatment, time and interaction of time and treatment. We will also present the summary statistics of voiding at each visit and change from baseline at each postdose time point. Difference in change and corresponding 95% confidence interval from baseline for each treatment group vs. placebo and 24,000 µg vs. 16,000 µg will also be presented in Table 14.2.1.1.

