9.2. Secondary Efficacy Analyses

Change in the mean number of urge incontinence episodes per 24 hours, change in mean number of urgency episodes, and change in the mean volume voided per micturition will be analyzed similarly as the primary efficacy endpoint and presented in Tables 14.2.1.2 through 14.2.1.4. Change in weight of 72 hour pad test and change in residual volume from bladder scan will also be analyzed and presented similarly in Tables 14.2.2 and 14.2.3 respectively.

Definitions of cystometric parameters are displayed in Table 2. The site readings and many of the overreader readings will be presented by subject in listings. Five of the overreader parameters will be analyzed, variables 1, 2, 3, 4 and 12, are displayed in [Table 2](#). The corresponding output table numbers and titles for these 5 variables are displayed in [Table 3](#). We may do additional exploratory analyses for additional cytometry parameters, if necessary.

Table 2: Cystometric Parameters and Definitions

Parameter	Description	Definition
DO; Yes/No	Detrusor overactivity ≥ 5 cm H ₂ O	Any involuntary contraction that has a pressure $> / = 5$ cm H ₂ O (INCLUSION CRITERIA) ^a
V _{First des} (mL)	Volume at first desire to void	The volume attained during filling cystometry that would lead the patient to pass urine at the next convenient moment but voiding can be delayed if necessary (ICS definition). ^a
P _{det. open} (cm H ₂ O)	Detrusor pressure at beginning of voiding (prior to onset of first contraction (either volitional or involuntary)	Detrusor pressure at onset of the first detrusor contraction (either volitional or involuntary). ^a
V _{1st} (mL)	Volume at first involuntary contraction; if detrusor overactivity (DO) present. Not applicable if no DO present.	Volume infused at the point of maximum detrusor pressure during the 1 st contraction. ^{a,b}
Det _{freq}	Total number of detrusor contractions during procedure (voluntary AND involuntary)	Total number of detrusor contractions including voluntary AND involuntary ^c
Leak (Yes/no)	Was there a leak with overactivity	Involuntary detrusor contractions resulting in leak (NOT counting voluntary voids) ^c
DO _{Leak freq}	Number of involuntary detrusor contractions resulting in leak (if DO present)	Number of involuntary detrusor contractions resulting in leak (if DO present) ^{b,c}
V _{leak} (mL)	If yes, Volume of each leak	Volume of each leak for each episode of leak ^{c,d}

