10. SAFETY ANALYSES

The safety analysis will be performed based on the Safety Population. Safety variables include AEs, clinical laboratory parameters, vital signs, physical examinations, and ECG.

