10.5. Other Safety Measures

None.

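### No planned safety table summarises post-dose residual volume, so a raised residual that is not reported as an adverse event appears only in a listing and a mean-change efficacy table

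*SAP*

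**What the plan says.** - **Measurement.** Protocol 6.4 schedules bladder scans at V1 (screening), V4, V6 and V8 (weeks 2, 8 and 24).
- **Use in the protocol.** Entry needs "Bladder scan or direct catheter drainage demonstrating a residual volume of" 200 mL or less (Protocol 4.2; exclusion 25 in 4.3 mirrors it). Stopping rule 1 in Protocol 5.2.1 covers urinary retention and includes a bladder volume "greater than 400 ml established by bladder scan". That volume is one of three joint conditions; the others are no voiding for more than 12 hours and the need for a drainage catheter.
- **Analysis.** SAP 9.2 states that "change in residual volume from bladder scan will also be analyzed and presented similarly" in Table 14.2.3, following the primary efficacy method of SAP 9.1. SAP 7.5 adds "Last observation carried forward (LOCF) will be used to impute efficacy endpoints". The Efficacy Population applies: "This population include subjects who are dosed and have at least one post-dose efficacy assessment".
- **Individual data.** SAP 9.1: "The bladder scan per subject will be detailed in Listing 16.2.6.3".
- **Safety section.** SAP 10: "Safety variables include AEs, clinical laboratory parameters, vital signs, physical examinations, and ECG". The only entry under "10.5. Other Safety Measures" is None.
- **Origin of the classification.** Neither the efficacy lists (Protocol 2.1 and 10.3) nor the safety lists (2.1 and 10.2) name residual volume. The SAP placed it under efficacy, while SAP 14 records no changes from the protocol.

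**The concern.** The product is intended to reduce detrusor contractility, and Protocol 5.2.1 names altered smooth-muscle function as a potential toxicity. Poor emptying is therefore a plausible harm, and the scan is the scheduled measurement closest to it. The primary question is safety, in groups of six. There the realistic signal is one or two affected participants, not a shift in the mean.

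A mean-change analysis is poorly suited to showing that. The report could conclude that residual volume did not differ between groups although one treated participant had a very large residual, and no safety table would prompt a reader to look for her.

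**Working it through.** The plan gives no figure of its own on this point. The check follows the possible routes into the tables and then sizes the dilution.

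**Routes for a high post-dose residual**

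1. *Retention meeting stopping rule 1.* It fits the adverse-event definition (Protocol 9.2), must be recorded (9.6), and enters Tables 14.3.1.1 and 14.3.1.2 (SAP 10.1). It also halts accrual pending DSMB and FDA review (5.2.1).
2. *Large residual in a participant who still voids.* Rule 1 is not met. Clinically significant findings are directed to adverse-event reporting for laboratory tests (SAP 10.2), physical examination (Protocol 6.5.1) and vital signs (6.5.3). No such sentence covers the scan. Appendix A has no row for residual volume or retention, although Protocol 9.5 allows unlisted events to be graded by general criteria once reported.
3. *The same participant, not reported.* Her value is in Listing 16.2.6.3 and contributes to Table 14.2.3. For continuous variables SAP 13.2 guarantees N, mean and SD. Minimum and maximum are promised for laboratory tests and vital signs (SAP 10.2, 10.3), not for residual volume.
4. *Catheterised residual at cystometry (V5, V8).* SAP Table 2 marks it as listed, not analysed.

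**Dilution in the mean**

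Shift in mean change from one participant = (peak − baseline)/n. The documents give no baseline residuals, so 0 to 100 mL is assumed.

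| Peak | n = 6 (one dose) | n = 12 (pooled active) |
|---|---|---|
| 401 mL | 301/6 to 401/6 = 50.2 to 66.8 mL | 301/12 to 401/12 = 25.1 to 33.4 mL |
| 201 mL | 101/6 to 201/6 = 16.8 to 33.5 mL | 101/12 to 201/12 = 8.4 to 16.8 mL |

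**What a test would show**

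Assume one participant rises from 50 to 401 mL (+351) and nobody else changes. A two-sample t-test stands in for the SAP's mixed model.

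- 6 active vs 6 placebo: mean difference 351/6 = 58.5 mL; active SD 143.3; pooled variance 143.3²/2 = 10,267; SE = √(10,267 × 2/6) = 58.5; t = 1.00 on 10 df; p about 0.34.
- 12 active vs 6 placebo: mean difference 351/12 = 29.25 mL; pooled variance = 351² × (11/12)/16 = 7,058; SE = √(7,058 × (1/12 + 1/6)) = 42.0; t = 0.70 on 16 df; p about 0.50.

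With everyone else unchanged, t does not depend on how large the rise is, because the difference and its SE scale together. A larger single rise would give the same p-value.

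**What a count would show**

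- One case in 6: 16.7% (exact 95% CI 0.4% to 64.1%). One in 12: 8.3% (0.2% to 38.5%).
- Chance of at least one case among 12, 1 − (1 − p)^12: 0.46, 0.72 and 0.93 at assumed true rates of 5%, 10% and 20%.
- No case in 12 still leaves a one-sided 95% upper bound of 1 − 0.05^(1/12) = 22.1%.

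**Precedent in the SAP**

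SAP 10.4 counts participants with QTcF above 450, 480 and 500 ms. The lowest and highest cut-offs correspond to the QTc exclusion limit (Protocol 4.3, item 22) and the ECG monitoring limit (Protocol 9.6). Residual volume has no counterpart.

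**The case against.** A reader might infer that a participant who passes the protocol's 200 or 400 mL limit appears in no safety table. The documents do not support that. Retention under rule 1 is a reportable adverse event. The 200 mL figure governs entry only, and 400 mL is one limb of a three-part rule for someone who cannot void. Neither is a stand-alone limit for a post-void residual, so a participant who voids and has 401 mL left has breached nothing.

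Other points for the plan:

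- *Eighteen participants can be read from a listing.* True, and the protocol prefers individual assessment of outliers for its named safety parameters. But that assessment is to be supported by descriptive statistics, and a listing is not a summary by group.
- *The population hardly matters.* Correct. Anyone with a post-dose scan is already in the Efficacy Population, so changing it adds no case.
- *Carrying values forward works both ways.* Correct. It can carry a high value as well as a low one, and Protocol 8.2 asks withdrawing participants for the Visit 8 procedures. The harm is confined to missed scans.
- *The illustration is stylised.* It is. The SAP's p-values are nominal, and an SD of 143 against 0 would itself draw attention. Real variation among the others would make the contrast less stark.
- *Layouts are in a separate shells document.* A minimum, maximum or flag there cannot be excluded; the SAP text does not promise one.
- *SAP 7.1 says no statistical analyses are made for DSMB reviews.* That limits the request to descriptive values.

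**Conclusion.** The point stands in a limited form. The SAP plans no safety summary of post-dose residual volume. The exposed case is specific: a raised residual, in a participant who still voids, that the investigator does not report as an adverse event. She would appear in Listing 16.2.6.3 and within a group mean. A single residual of 401 mL moves that mean by about 50 to 67 mL in a dose group, or 25 to 33 mL in pooled active, under the assumed baseline of 0 to 100 mL. The p-values of 0.34 and 0.50 also assume no change in anyone else and a t-test in place of the mixed model.

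This does not invalidate the plan and does not mean that a stopping event would be missed. It is an inexpensive improvement worth making, because the trial's primary question is safety and the SAP already uses threshold counts for QTcF.

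**What to change.** In SAP 10.5, replace None with one descriptive table on the Safety Population, using observed values only (no carrying forward):

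- by visit (V4, V6, V8 and any unscheduled scan) and by group (placebo, 16,000 µg, 24,000 µg, pooled active);
- number and percentage with residual above 200 mL and above 400 mL;
- each participant's maximum post-dose value.

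State in a footnote that the cut-offs are reference values taken from the entry limit and from the volume in stopping rule 1, and are not stand-alone stopping limits. List the catheterised residuals from cystometry (V5, V8) alongside. Table 14.2.3 may stay as a supplement.

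Class the scans as safety data, so that available values are included descriptively in the data the DSMB sees under Protocol 5.2.2. At the 4-week review the last participant in a cohort would have only her V4 scan, because V6 falls at week 8. No inferential analysis is added, so SAP 7.1 can stand.

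The cost is one additional descriptive table from data already collected, with no new procedure and no change to any clinical rule.

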10.3 Efficacy

The sample size has been estimated assuming a standard deviation of 2.5 and a two sample t-test to have 80% power.

The protocol is designed to observe a 30% reduction in the number of voids compared to placebo following gene transfer using the following calculations with NCSS/PASS program (NCSS, Kaysville, Utah, 84037-3233).

Table 10;. Powering									
Power	N1	N2	Ratio	Alph	Beta	Mean	Mean2	S1	S2
0.80251	9	10	1.111	0.050	0.19749	10.0	6.6	2.5	2.5

The mean number of micturations per 24 hours will be evaluated at all visits and changes compared to baseline and placebo.

The other secondary outcome measures will be the change in the mean number of urge incontinence episodes per 24 hours; urgency episodes per 24 hours; mean volume voided per micturition, diminished urgency perception; change in weight of 72 hour pad test; and change in

detrusor overactivity (DO) including peak amplitude, volume at which DO appears and presence or absence of DO. The participants' perception of their bladder condition and response to treatment will be assessed at baseline (Week 0) and after 1, 2, 4, 8, 12, and 24 weeks. Improvement will be defined as a decrease of 1 point or more from baseline. Quality of Life (QoL) will be evaluated using the Kings Health Questionnaire (see Appendix B for algorithm). Change in maximum bladder capacity (difference of pre-treatment to post-treatment volume) as determined by cystometry of *hMaxi-K* versus pool of placebo participants from each treatment level.

Participants will be assessed for changes from baseline in urinary symptoms following administration of *hMaxi-K* using the questions of the ICIQ-SF form and the urgency rating scale. Participants will also be pooled across treatment groups (all active vs. all placebo).

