V _{leak cum} (mL)	If yes, cumulative volume of ALL leaks during procedure	Cumulative volume of leaks (calculated by computer from individual volumes) ^{c,d}
DO _{No Leak freq}	Number of involuntary detrusor contractions NOT resulting in leak	Total number of involuntary detrusor contractions that do not have an associated leak ^{b,c}
P _{det Max} (cm H ₂ O)	Maximum detrusor pressure at involuntary contraction	Maximum amplitude of detrusor contraction during an involuntary contraction (if present) ^{c,e}
P _{det 1st} (cm H ₂ O)	Maximum detrusor pressure at FIRST contraction	Max detrusor pressure at FIRST contraction (voluntary or involuntary) ^{a,b}
P _{Det Any} (cm H ₂ O)	Maximum detrusor pressure at ANY contraction	MAXIMUM detrusor pressure attained during the entire study (voluntary or involuntary) ^{c,f}
Cys Cap (mL)	Cystometric Capacity: Volume at strong urge to void	The volume at which the patient feels that he/she can no longer delay micturition (has a strong desire to void). ^c (ICS definition)

Table 2: Cystometric Parameters and Definitions (Continued)

Parameter	Description	Definition
Q_{max} (mL / sec)	Peak flow rate during voiding (for both leaks and voluntary voids)	The Maximum rate of flow during any void (for both involuntary and voluntary voids) ^c
V_{voided} (mL)	Total voided volume (leaks and voluntary)	Total volume voided for leak and volitional voids during the procedure ^c
PVR (mL)	Post Void Residual Volume (PVR) (from catheterization)	Volume left in bladder after voiding at the conclusion of the study. This is measured by urodynamic catheterization ^c
$(V_{total\ bladder})$ (mL)	Total Bladder Volume (Total voided volume +catheterized PVR)	Post void residual volume + total voided volume (will be calculated) ^c
DO _{dur} (seconds)	Duration of detrusor overactivity	Duration of MAXIMUM detrusor activity ^{c,d}
P_{Det}, Q_{Max} (cm H ₂ O)	Detrusor pressure at maximum flow during an involuntary contraction	Maximum detrusor pressure during terminal void (voluntary or involuntary) ^{c,d}
$V_{bladder\ DO}$ (mL)	Bladder volume at each involuntary detrusor contraction	Infused bladder volume at the peak pressure of each involuntary contraction minus the amount leaked at each point for each involuntary contraction; Total will be calculated by the computer ^{c,d}

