P_{abd} (cm H ₂ O)	Maximum abdominal pressure during any contraction	MAXIMUM abdominal pressure during ANY contraction. This will assess the abdominal straining component to voiding ^{c,d}
a To be analyzed b This is done by overreader, but not the sites c Listing only; not analyzed d Done by site only e Detrusor pressure at first involuntary contraction is called “ Detrusor Pressure ” for sites on eCRF. f Maximum detrusor pressure at ANY contraction is called “ Maximum Detrusor Pressure ” for sites on eCRF.		

The Cystometry overread parameters will be used for objective evaluation analyses. Binary outcomes will be estimated using generalized estimating equation (GEE) model with binary distribution and a logistic link clustered by participant. The parameters that can be treated as continuous variables will be analyzed similarly to the primary efficacy endpoint using linear mixed effect model adjusting for clustering effect by participants.

The mapping of the cystometry parameters that will be analyzed and the corresponding tables that will be used to present the results are shown in [Table 3](#).

Table 3: Cystometry Parameter Analysis Endpoints and Tables that will present the Analysis Results

1) Detrusor overactivity ≥ 5 cm H ₂ O (yes/no- INCLUSION CRITERIA)	Table 14.2.4.1: Cystometry Overread: Change in the Presence and Absence of Detrusor Overactivity (DO)
2) Volume at first desire to void	Table 14.2.4.2: Cystometry Overread: Change of Volume at First Desire to Void (mL)
3) Detrusor pressure at beginning of voiding (prior to onset of first contraction (either volitional or involuntary))	Table 14.2.4.3: Cystometry Overread: Change from Baseline for Detrusor Pressure Prior To Onset of First Contraction (Either Volitional Or Involuntary) (cm H ₂ O)
4) Volume at first involuntary contraction; if detrusor overactivity (DO) present-Not applicable if no DO present	Table 14.2.4.4: Cystometry Overread: Change from Baseline for Volume of First Involuntary Detrusor Contraction (mL) in Presence of Detrusor Overactivity
5) Maximum detrusor pressure at FIRST contraction	Table 14.2.4.5: Cystometry Overread: Change of Maximum Detrusor Pressure at FIRST Contraction (Voluntary or Involuntary) (cm H ₂ O)

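### The SAP's detrusor-pressure endpoint mixes voluntary and involuntary contractions, and peak amplitude of detrusor overactivity has no planned analysis

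*SAP*

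**What the plan says.** On cystometry, SAP 9.2 states: "Five of the overreader parameters will be analyzed, variables 1, 2, 3, 4 and 12". Variable 12 in SAP Table 2 is P det 1st, defined as "Max detrusor pressure at FIRST contraction (voluntary or involuntary". Its footnotes mark it for analysis and as read by the overreader, not the sites. SAP Table 3 sends it to output Table 14.2.4.5, whose title repeats the mixture: "Change of Maximum Detrusor Pressure at FIRST Contraction (Voluntary or Involuntary". Continuous cystometry parameters go into the linear mixed model used for the number of voids. Nothing in that model refers to the type of contraction.

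SAP Table 2 also contains P det Max: "Maximum amplitude of detrusor contraction during an involuntary contraction (if present". Its footnote c reads "Listing only; not analyzed".

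Protocol 10.3 names, among the secondary outcomes, change in "detrusor overactivity (DO) including peak amplitude, volume at which DO appears and presence or absence of DO". SAP Table 3 has an output table for presence or absence of DO (14.2.4.1) and one for volume at the first involuntary contraction (14.2.4.4). It has none for amplitude. SAP section 14, which should list changes from the protocol's methods, reports none.

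**The concern.** A change from baseline is interpretable only if the same thing is measured both times. P det 1st meets that condition while the first contraction stays involuntary. It fails in the participants in whom the drug does what SAP 4.4.2 hypothesises, namely reduces DO. In a participant with no DO left, the first contraction is the void, and its pressure reflects voiding rather than overactivity.

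Two things are at stake. First, Table 14.2.4.5 could be read as evidence about the strength of overactivity when part of it reflects a change of event, and it could appear to contradict the DO table beside it. Second, a component that the protocol names is left without a planned analysis, and the departure is not declared.

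The SAP handles this issue for volume: V 1st is not applicable when no DO is present. P det 1st carries no such condition.

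**Working it through.** The plan states no figure for this endpoint, so there is nothing to reproduce. The check has two parts: whether the switch of event follows from the design, and how it would act on the means.

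**Does the switch follow from the design?**

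1. Inclusion criterion 3 (Protocol 4.2) requires at least one involuntary contraction of at least 5 cm H2O at Visit 1A. This is the baseline cystometry.
2. SAP 4.4.2 puts the filling study before the pressure-flow study. Protocol Appendix D tells participants neither to void nor to inhibit voiding during filling. The first contraction at baseline is therefore expected to be involuntary.
3. If there is no DO at Week 4 or 24, the first contraction is the voluntary void.

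**How does it act on the means?**

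Let I be the baseline involuntary amplitude, V the voluntary voiding pressure, f the fraction of an arm losing DO, and r the proportional fall in amplitude in those who keep DO.

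- Mean change in P det 1st = f(V − I) − (1 − f)rI
- Mean change in peak DO amplitude, scoring absent DO as 0 = −fI − (1 − f)rI

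The only human pressure in the documents that bears on I or V is the 5 cm H2O threshold. The ranges I = 5 to 40 and V = 15 to 40 cm H2O are assumptions for illustration.

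| I | V | f | r | Change in P det 1st | Change in peak DO amplitude |
|---|---|---|---|---|---|
| 10 | 25 | 0.5 | 0 | 0.5 × 15 = +7.5 | −0.5 × 10 = −5.0 |
| 20 | 40 | 0.5 | 0.3 | 10 − 3 = +7.0 | −10 − 3 = −13.0 |
| 40 | 40 | 0.5 | 0 | 0.5 × 0 = 0 | −0.5 × 40 = −20.0 |
| 30 | 25 | 0.5 | 0 | 0.5 × (−5) = −2.5 | −0.5 × 30 = −15.0 |
| 40 | 25 | 1 | – | −15 | −40 |

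Peak DO amplitude falls in every row. P det 1st rises, stays level or falls, and under full abolition its sign depends only on whether V exceeds I.

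**Size per participant.** In an arm of six, one switch moves the mean by (V − I)/6. Over the assumed ranges V − I runs from 15 − 40 = −25 to 40 − 5 = +35, so one switch moves the mean by −4.2 to +5.8 cm H2O. In the pooled active group of 12 the divisor is 12, giving −2.1 to +2.9.

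**Size in the planned contrast.** The comparison is with combined placebo (N = 6). At one visit with complete data, and with V − I the same in both arms, the switch contributes (f_active − f_placebo)(V − I):

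- 3 of 6 active and 0 of 6 placebo lose DO: 0.5 × (−25 to +35) = −12.5 to +17.5 cm H2O
- 3 of 6 active and 1 of 6 placebo: (2/6) × (−25 to +35) = −8.3 to +11.7 cm H2O
- equal fractions: 0

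**The case against.** The strongest reply is that little depends on this variable. The trial is a Phase 1 safety study, SAP 7.3 calls the efficacy part exploratory with nominal p-values, and no escalation rule uses detrusor pressure. The list of individual efficacy endpoints in the protocol's Objectives section omits DO amplitude. Protocol 10.4 says that methods will be updated and finalised in the SAP. Loss of DO is analysed directly in Table 14.2.4.1, the title of Table 14.2.4.5 discloses the mixture, individual overread values are listed, and SAP 9.2 leaves room for further exploratory cystometry analyses. All of this stands and limits the importance of the point. It does not supply an amplitude analysis, because the exploratory clause names no parameter, and it does not make the pooled change interpretable.

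A reader might infer more than the documents support, in three ways:

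- **That responders will show a pressure increase.** This requires voluntary pressure to exceed baseline involuntary amplitude, which no human figure in the documents establishes. SAP Table 2 also allows the terminal void to be involuntary. In such a participant the baseline first contraction could itself be the void, which would narrow the gap.
- **That the protocol's DO outcome is not analysed.** Two of its three named components are.
- **That P det Max should simply replace P det 1st.** SAP Table 2 defines P det Max as a maximum amplitude, but its footnote e refers to the first involuntary contraction, so it is unclear which contraction is recorded. That an overread value exists is inferred from the absence of the site-only footnote. The SAP does not say so outright.

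**Conclusion.** The point holds in a limited form. In participants who lose DO, change in P det 1st compares two different events, so the pooled change is not a measure of DO amplitude and can move in either direction. This rests on the entry criterion, the order of the test and the definition of the variable, and needs no assumed pressures. The sizes in cm H2O do need them: they depend on assumed amplitudes and on the difference between arms in the fraction losing DO, and they vanish if that difference is zero.

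Separately, peak DO amplitude has no planned analysis although Protocol 10.3 names it, and SAP section 14 does not record the omission. Neither point touches the safety objective. Both concern a secondary efficacy variable and are worth settling before the blind is broken. P det open, also analysed, is likewise defined over either kind of contraction and deserves the same look.

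**What to change.** In SAP 9.2, Table 2 and Table 3:

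1. Add a planned output table for change in overread P det Max, involuntary contractions only. State whether it is the first or the largest involuntary contraction, and reconcile footnote e with that choice. Confirm that the overreader records it.
2. Score a participant with a completed cystometry and no DO as 0 (lowest rank), and compare arms with a rank-based test. Say that this 0 is an observed value, so that the last-observation-carried-forward rule in SAP 7.5 does not overwrite it.
3. Keep P det 1st, but report it by contraction type (voluntary or involuntary) at each visit, and do not present the pooled change as a DO outcome.
4. Record any remaining departure from Protocol 10.3 in section 14, and make the SAP synopsis and section 3.2, which repeat the five parameters, agree.

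The cost is SAP wording and one more table shell, with no new procedure for participants. The drawbacks are a spike at zero, which is why a rank-based comparison is preferred to the mixed model here, and partial overlap with the binary DO endpoint.
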